5.2 PACKAGING, LABELING, SUPPLY AND STORAGE

5.2.1 Packaging and Labeling

The Study Vaccine will be packaged and labeled according to current International Conference on Harmonisation (ICH) Good Manufacturing Practice and GCP guidelines, and national legal requirements.

The manufacture and labeling of the Study Vaccine will comply with specific US Regulatory requirements.

5.2.2 Supply and Storage

The Study Vaccines will be supplied to the study sites by Seqirus or a third party vendor contracted by Seqirus. Syringes will be labeled and boxed in individual cartons.

The Study Vaccines should be stored under temperature monitored conditions (+36°F to +46°F [+2°C to +8°C]) in a secure area. Under no circumstances should the vaccines be frozen, as this may disrupt the antigenic immunogenicity of the viral proteins. If the container contents are frozen, or suspected to have been frozen, the product should not be used. In order to protect from light, the vaccine must be stored in its original carton until time of administration.

5.3 ACCOUNTABILITY AND DESTRUCTION

Initial shipments of Study Vaccine will be shipped to the investigational study sites on confirmation that regulatory and Institutional Review Board (IRB) requirements have been met and will be available prior to study start. Upon receipt of the Study Vaccine, the Investigator/delegate will conduct an inventory and acknowledge receipt of the product.

Study Vaccines must only be used for subjects enrolled in this clinical study. The appropriately qualified unblinded site staff member administering the Study Vaccine must record the dispensing details on the Study Vaccine Administration Form provided. On completion of the study, delivery records will be reconciled with those of used and unused Study Vaccine.

Used syringes are to be disposed of immediately after use in appropriate sharps containers. Used cartons are to be retained for accountability purposes and are to be destroyed at site after final accountability/reconciliation has been completed at the site. Unused vaccines are to be returned to the third party vendor responsible for vaccine management for final disposal or destroyed at site provided a certificate of destruction is supplied. All relevant disposal documentation, including the certificate of destruction, will be filed in the TMF and a copy filed-in the investigational site files.

Information on the destruction of the Study Vaccine is provided in the Pharmacy Manual.

5.4 OTHER INTERVENTION(S)

Not applicable.

5.5 RESCUE THERAPY

Not applicable.

6 ALLOCATION, DOSING AND ADMINISTRATION

6.1 ALLOCATION TO TREATMENT

6.1.1 Subject Assignment

After providing written informed consent, the subject will be issued with a study-level unique subject identification number. The subject identification number will be used to identify the subject for the duration of the study. Subject identification numbers will not be reassigned or reused.

6.1.2 Randomization Procedures

A randomization scheme will be used to ensure that the balance between the treatment groups is maintained. To ensure the study blind is maintained, delegates from the Interactive Response Technology (IRT) company, in association with a Seqirus statistician/delegate not directly involved in the analysis of study results, will prepare the study randomization code. The Stability and Environmental Monitoring group at Seqirus will keep a checked final copy of the randomization code on file. Emergency Code Break IRT access will be provided to the investigational site for use in case of an emergency.

Subjects in the 36 through 59 months age group will be enrolled and randomized first until approximately one third of subjects (or a minimum of 300 subjects) in this age cohort have received the first vaccination and have had an opportunity to enter at least 7 days of safety data postvaccination. A safety data cut will then be performed and a DSMB meeting convened to review and assess the available safety data. Recruitment in the 36 through 59 months age cohort will not be halted during the period of the data cut and DSMB review. Enrollment in the younger age cohort (subjects 6 months through 35 months of age) will only commence after the DSMB has reviewed the safety data and recommended that the study may proceed.

A second safety data cut will be performed when approximately one third of subjects (or a minimum of 300 subjects) in the 6 through to 35 months age cohort have received the first

vaccination and have had an opportunity to enter at least 7 days of safety data postvaccination. A DSMB meeting will be convened once tables and listings are produced to review and assess the available safety data. Recruitment in the 6 through 35 months age cohort will not be halted during the period of the data cut and DSMB review.

Eligible subjects will be randomized by means of IRT to one of the 2 treatment groups in a 3:1 ratio (Seqirus QIV: Comparator QIV) and will be proportionally balanced in the two age strata (6 through 35 months and 36 through 59 months), with no more than 60% of the total sample size represented in one age stratum. The IRT system will manage randomization and provide to the sites a subject randomization number. The number will correspond to the appropriate study treatment.

The Investigator will be supplied with a user guide for the IRT.

6.1.3 Blinding Procedures

6.1.3.1 *Blinding Method*

Investigational site staff including the investigator and all personnel performing study assessments will be blinded to treatment allocation (observer-blind). The subject and parent(s)/ guardian(s) will also remain blinded to treatment allocation.

As there may be a visual difference between the Seqirus QIV and the Comparator QIV pre-filled syringes, personnel who prepare and administer the Study Vaccine will be considered unblinded and excluded from involvement in other study procedures, with the exception of other Study Vaccine related activities, such as receipt, preparation and accountability management.

All Seqirus study staff, excluding those in the Seqirus Stability and Environmental Monitoring group and Quality Assurance group, will also be blinded to treatment allocation. Study monitors will be blinded to subject treatment allocation and will remain blinded when performing Study Vaccine accountability.

6.1.3.2 *Breaking the Blind for an Emergency*

The randomization code for individual subjects may be unblinded to a site via the IRT system during the study in emergency situations for reasons of subject safety, if knowing the treatment assignment will change subject management. Whenever possible, the Investigator should consult with the Medical Monitor before unblinding the randomization code. The reason for unblinding the randomization code must be fully documented and the Investigator must follow the defined procedures provided in the Study Manual.

6.1.3.3 *Planned Unblinding Procedures*

The randomization code will be unblinded four times:

1. at the time of the safety analysis after a third of subjects or a minimum of 300 subjects in the 36 months through 59 months of age cohort have been enrolled;
2. at the time of the safety analysis after a third of subjects or a minimum of 300 subjects in the 6 months through 35 months of age cohort have been enrolled
3. at the time of the interim analysis when all subjects have completed all immunogenicity assessments and all solicited and unsolicited adverse event reporting;
4. and finally, once all data (including extended follow-up for recording SAEs and AESIs) have been entered into the study database for each subject and the database has been locked.

The randomization code will be provided to the Biostatistics group once written authorization of database lock has been received.

The first unblinding will occur after a third of subjects or a minimum of 300 subjects in the 36 months through 59 months of age cohort are enrolled. The DSMB will review and assess available unblinded safety data in a closed session. The Seqirus team will remain blinded.

The second unblinding will occur after a third of subjects or a minimum of 300 subjects in the 6 months through 35 months of age cohort are enrolled. The DSMB will review and assess available unblinded safety data in a closed session. The Seqirus team will remain blinded.

Unblinding of the randomization code will also occur once all subjects have completed all immunogenicity assessments and all solicited and unsolicited adverse event reporting. This will facilitate timely analysis of immunogenicity and safety data including all solicited AEs. The results may be communicated to regulatory authorities and relevant personnel within Seqirus but not to personnel directly involved in monitoring the study or interacting with investigators. The results will not be communicated to investigators.

A final clinical study report will present all immunogenicity and safety data collected from the active study period and safety data through to the final evaluation (180 days following the last vaccination dose).

Seqirus Safety personnel may unblind the randomization code for an individual subject at any time to facilitate assessment of suspected unexpected serious adverse reactions (SUSARs) experienced by any subject for expedited reporting to regulatory authorities. To maintain integrity of the study blind the Seqirus Safety personnel responsible for assessment of SUSARs are excluded from the Seqirus study team.

6.2 DOSING AND ADMINISTRATION

An appropriately qualified unblinded site staff member will dispense and administer the Study Vaccine as a 0.25 or mL 0.5mL intramuscular dose as appropriate into either right or left deltoid muscle or into the anterolateral aspect of the thigh, according to the randomization code and the age of the subject. Prior to administering a study vaccine the prefilled syringe should be shaken thoroughly and inspected visually for particulate matter and discoloration. If either of those conditions exist, the study vaccine should not be administered. Where possible, the injection will be administered into the contralateral arm to which the blood sample was drawn, unless there is a medical reason which dictates both need to be conducted on the same arm. This reason should be documented in source, if applicable.

The use of topical anesthetic cream (eg, EMLA Cream) on the vaccination site before or after administration of the Study Vaccine is prohibited.

6.3 TREATMENT COMPLIANCE

Not applicable. Study Vaccine will be administered by site staff.

7 CONTRAINDICATIONS, PERMITTED THERAPIES AND PROHIBITED THERAPIES

7.1 CONTRAINDICATIONS AND PRECAUTIONS TO FURTHER DOSING

Administration of the second vaccination will be postponed in the event individual subject is experiencing clinical signs/symptoms of active infection and/or axillary temperature of $\geq 99.5^{\circ}\text{F}$ ($\geq 37.5^{\circ}\text{C}$) on the day of vaccination or within 48 hours preceding vaccination. Vaccination also will be postponed if individual subject used a prophylactic antipyretic on the day of vaccination.

Administration of the second vaccination to individual subjects will be contraindicated in the event of:

1. Axillary temperature of greater than 103.1°F (39.5°C) within 48 hours of the first vaccination, and assessed as related to study vaccination;
2. Collapse or shock-like state (hypotonic-hyporesponsive episode) within 48 hours of the first vaccination, and assessed as related to study vaccination;
3. Seizures with or without fever after the first vaccination, and assessed as related to study vaccination;
4. Any other event related to the Study Vaccine, and considered by the Investigator and/or the Sponsor to be clinically significant, and which would suggest significant hazard with further administration of Study Vaccine.

Subjects who are contraindicated to receive the second vaccination should complete an Exit Visit for assessment by the Investigator/ delegate.

7.2 PERMITTED THERAPIES

Therapies not listed in Section 7.3 below are permitted during the study.

7.3 PROHIBITED THERAPIES

Subjects are not to be enrolled into the study if they receive any prohibited therapy or any therapy in a prohibited dosage that cannot be discontinued or reduced to a permitted dose before enrollment. Therapies not listed below are permitted.

The following therapies are NOT PERMITTED before and/or during the active study period (Day 1 to Exit Visit) for the periods outlined below and as specified in the study exclusion criteria:

- Current or recent immunosuppressive or immunomodulatory therapy, as follows:
 - Chronic or long term systemic corticosteroids: ≥ 0.125 mg/kg/day of oral prednisolone or equivalent daily;
 - Sporadic systemic corticosteroids: ≥ 0.5 mg/kg/day of oral prednisolone or equivalent for one or more short courses of > 3 days in the three months preceding vaccination and/or during the active study period.
- Administration of immunoglobulin and/or any blood products within the 3 months preceding study vaccination, or planned administration during the active study period;
- Participation in a clinical trial or use of an investigational compound (ie, a new chemical or biological entity not licensed for clinical use) within 28 days prior to the first dose of Study Vaccine, or within 28 days after receiving the final indicated dose of Study Vaccine, or plans to enter a clinical trial during this period;
- Vaccination with a licensed or investigational influenza vaccine within the 6 months prior to receiving the first dose of Study Vaccine and during the study;
- Vaccination with a licensed live or inactivated vaccine 21 days prior to receiving the Study Vaccine, or plans to receive any licensed vaccine prior to the Study Exit Visit;
- Treatment with warfarin or other anticoagulants in the 3 weeks preceding vaccination, contraindicating intramuscular vaccination (with the exception of antiplatelet agents).
- Prophylactic antipyretics on the day of vaccination or for the first 7 days postvaccination. Antipyretic use for the treatment of AEs during the study period is permitted, and will be documented as concomitant medications.
- The use of topical anesthetic cream (eg, EMLA Cream) on the vaccination site before or after administration of the Study Vaccine is prohibited. Topical anesthetic cream use at the blood draw site is permitted.

If any of the above therapies are received during the active study period, the subject will not be withdrawn from the study unless required for medical reasons, but immunogenicity results pertaining to this subject may be excluded from assessment prior to unblinding following medical review of the potential for the therapies to impact on immunogenicity results.

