8.3 CONCOMITANT THERAPIES

All drugs and/or procedures (including any physician-prescribed dietary supplement or vitamin), currently being administered to a subject at the time of signing informed consent, and which continue to be taken in addition to the Study Vaccine during the Active Study Period, are regarded as concomitant therapies and must be documented as such in the eCRF. Concomitant medications that are being taken at the time of study enrollment should be initially recorded, and the reason for medication being taken should be recorded. At subsequent visits, any concomitant medications used during the active study period (from Day 1 until Exit Visit) should be recorded, and the reason for medication should be recorded. After the active study period, it is no longer necessary to routinely seek information on concomitant medications. However, if an SAE occurs after the Exit Visit, any medications

taken prior to and at the time of the SAE (whether or not related to the SAE) should be recorded.

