#### 4.7.4.2 Solicited Adverse Events

Solicited AEs are those events specifically sought for and recorded by the parent(s)/guardian(s) in the 7-Day Diary, entered on the day of vaccination and the subsequent 6 days.

Solicited Local AEs include pain, induration/swelling, and erythema/redness. All solicited local AEs will be assessed as related to the Study Vaccine.

Solicited Systemic AEs include fever (temperature  $\geq 37.5^{\circ}\text{C}$ ), nausea and/or vomiting, and diarrhea. For subjects less than 36 months of age at the time of the first dose of study vaccine solicited Systemic AEs also include loss of appetite and irritability. For subjects 36 months of age and older at the time of the first dose of study vaccine solicited Systemic AEs also include headache, myalgia, and malaise and fatigue.

For all solicited AEs the following summaries will be presented by treatment group. In addition, the summaries will be presented by dose (i.e. After 1st Vaccination, After 2nd Vaccination):

- The number and percentage of subjects reporting at least one occurrence of each type of adverse event will be presented with 95% CIs.
- The number and percentage of subjects experiencing at least one local reaction will be presented with 95% CIs.
- The number and percentage of subjects experiencing at least one systemic adverse event will be presented with 95% CIs.

For each of these summaries the relative risk and 95% CIs will be presented for Seqirus QIV/Comparator QIV.

All summaries will be presented overall and by maximum intensity. Analyses by treatment group will be repeated by age strata, by gender, by race, and by ethnicity where specified.

Separate summaries will be presented for Related Solicited Systemic Adverse Events, overall and by maximum intensity after any vaccination.

For all solicited events, the day of onset will be determined according to the day they are first recorded (day 1 to day 7). Summaries will be presented with the number (and percentage) of subjects experiencing at least one event by onset day.

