#### 4.7.5 Exploratory endpoints

The exploratory objective of the study is:

- To assess the frequency of antipyretic use in the first 7 days post-vaccination in two age strata: 6 months through to 35 months, and 36 months through 59 months, as well as overall according to treatment group.

Antipyretics are among medications coded under the WHO Drug dictionary ATC code N02B. Namely they include the following drug names:

- Ibuprofen
- Acetaminophen

The number and percentage of subjects consuming antipyretics during the time period Day 1 to Day 7 after each vaccination (1st and 2nd), and after any vaccination will be presented along with the exact 95% confidence limits and the number of medications used.

Descriptive statistics, i.e. number of observation, mean, SD, median, minimum, maximum will be presented to summarize the total days of individual antipyretics use in the subjects with antipyretics use. Summaries will be presented with the number (and percentage) of subjects by days of use.

Results will be presented by treatment, overall and by age strata.

Where a medication start date/end date is partially or fully missing, and it is unclear as to whether the medication is concomitant during the time period Day 1- Day 7 after each vaccination, it will be assumed that it is concomitant. Where it is unclear whether the medication has been taken in a day, it will be assumed that it has been taken.

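### Fevers suppressed by banned prophylactic antipyretics go unseen in the planned fever analysis, and the antipyretic table pools banned with permitted use on the Per-Protocol Population

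*Protocol*

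**What the plan says.** **The ban.** Protocol 7.3, repeated in SAP 3.4, lists among the therapies not permitted: "Prophylactic antipyretics on the day of vaccination or for the first 7 days postvaccination". The next sentence separates treatment from prophylaxis: "Antipyretic use for the treatment of AEs during the study period is permitted, and will be documented as concomitant medications".

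**What follows from a breach.**
- Protocol 7.3 keeps the child in the study, "but immunogenicity results pertaining to this subject may be excluded from assessment prior to unblinding". SAP 3.5.3, 3.5.4 and 4.10 carry this into the Evaluable and Per-Protocol Populations, and only where a medical review sees a possible effect on immunogenicity.
- Protocol 7.1, on the second dose: "Vaccination also will be postponed if individual subject used a prophylactic antipyretic on the day of vaccination".
- SAP 4.10.1 gives prohibited medication as an example of a major deviation, and SAP 4.10 lists all major deviations.

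**Fever.** The Solicited Safety Population (SAP 3.5.2.2 and 3.5.2.3) requires a dose and any solicited data. SAP 4.7.4.2 grades fever on recorded temperature, with less than 37.5°C as grade 0 and 38.5°C or more as grade 3. Of the solicited summaries it says: "For each of these summaries the relative risk and 95% CIs will be presented for Seqirus QIV/Comparator QIV".

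**Antipyretic use.** SAP 4.7.5 plans: "The number and percentage of subjects consuming antipyretics during the time period Day 1 to Day 7 after each vaccination". The table is not split by reason, although Protocol 8.3 says of concomitant medications "and the reason for medication should be recorded". SAP 3.5.4 assigns this analysis to the Per-Protocol Population.

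**The concern.** The ban spans the whole diary window in which solicited fever is measured, and fever is the diary outcome that prophylaxis acts on most directly. Yet no safety set, grading rule or planned sensitivity analysis refers to a breach.

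This matters because febrile reactions are the known paediatric signal for the sponsor's earlier trivalent vaccine, mainly in children from 6 months to under 5 years (Protocol 1.1.2 and 1.4), which is the age range studied here. Related fever of 38.5°C or more also feeds a 5% enrolment halting rule (Protocol 9.7).

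The antipyretic table should help a reader judge whether fever was masked, but it cannot as planned. Treatment use signals a reaction and prophylactic use may hide one, so a higher pooled rate could mean either. The table also runs on a set from which some users of banned antipyretics may already have been removed, and its denominator is not that of the fever tables.

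**Working it through.** **1. What a breach can change, place by place**

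| Place | Effect of prophylactic use |
|---|---|
| Evaluable and Per-Protocol sets (SAP 3.5.3, 3.5.4) | Exclusion if judged to affect immunogenicity |
| Second vaccination (Protocol 7.1) | Postponed, for use on vaccination day only |
| Deviations (SAP 4.10, 4.10.1) | Listed as major |
| Safety sets (SAP 3.5.2) | None stated |
| Fever grading and relative risk (SAP 4.7.4.2) | None stated |
| Missing-data rules (SAP 4.11) | None stated |
| Antipyretic table (SAP 4.7.5) | Counted with treatment use, if the child is still in the Per-Protocol set |

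**2. The plan's own figures.** The documents give none for fever or antipyretic use. Their only design calculation reproduces: SCR power per strain is 97.32%, 0.9732^4 = 89.70%, and 89.70% × 99.95% = 89.66%. It concerns immunogenicity and is not affected by this point.

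**3. Absolute fever rates.** Let p be the true fever rate, q the share of dose periods with prophylaxis and e the share of those fevers suppressed. The values of q and e are assumptions, here 2% to 20% and 50% to 100%.

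Observed rate = p × (1 − q·e)
- Smallest effect: 1 − 0.02 × 0.5 = 0.99. Largest: 1 − 0.20 × 1.0 = 0.80.
- A true 10% reads 9.9% to 8.0%.
- For the observed rate to reach the 5% halting threshold, the true rate must be 5%/0.99 = 5.05% to 5%/0.80 = 6.25%.

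**4. Equal use in both arms.** The factor cancels in the ratio. With assumed rates of 10% and 7%, the relative risk is 1.43 before and after. The risk difference of 3.0 points shrinks to 3.0 × 0.99 = 2.97, down to 3.0 × 0.80 = 2.4.

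**5. Unequal use.** The relative risk is multiplied by (1 − q_S·e)/(1 − q_C·e), where S is Seqirus QIV and C the comparator.
- 5% vs 2%: 0.975/0.99 = 0.985 (e = 0.5) and 0.95/0.98 = 0.969 (e = 1), so 1.43 becomes 1.41 or 1.38.
- 20% vs 10%: 0.90/0.95 = 0.947 and 0.80/0.90 = 0.889, so 1.43 becomes 1.35 or 1.27.

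**6. How unequal could dose 2 use be?** Suppose parents premedicate at dose 2 because of fever at dose 1. If a share m of children with dose 1 fever is premedicated, then q = m × (dose 1 fever rate), and the gap in q is at most the gap in dose 1 fever. With 10% vs 7% and m = 0.5, q is 5% vs 3.5%. At e = 0.5 the multiplier is 0.975/0.9825 = 0.99.

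**7. What a bound would show.** Counting every period with prophylaxis as febrile gives p(1 − q) + q.
- p = 10%, q = 2%: 9.8% + 2% = 11.8%. q = 20%: 8% + 20% = 28%.
- p = 7%, q = 2%: 6.86% + 2% = 8.86%. q = 20%: 5.6% + 20% = 25.6%.
- Relative risk under equal use: 11.8/8.86 = 1.33 and 28/25.6 = 1.09.

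So each arm's rate is bounded from above, but the ratio in that table is drawn towards 1 and is not an estimate.

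**The case against.** The plan is not without controls, and several of them work at dose 2. Same-day prophylaxis postpones the second vaccination, and related fever above 39.5°C within 48 hours of the first rules the second out (Protocol 7.1). Breaches are listed. Parents and assessors are blinded (Protocol 6.1.3.1), so similar use in both arms is plausible. Keeping every dosed child with data in the safety set is sound practice. The antipyretic endpoint is exploratory and no primary endpoint is touched.

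Most of this stands, and it limits the size of the problem. It does not close it. The postponement rule is written for the second dose and does not reach medication given after the injection or on later diary days. A listing changes no fever rate. Blinding does not prevent parents from reacting to a dose 1 fever that they saw.

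A reader might infer more than the documents support:
- *That a breach has no consequence outside immunogenicity.* Postponement and the deviation listing say otherwise.
- *That premedicated children are automatically counted as fever-free.* A child who reaches 37.5°C despite prophylaxis counts as febrile; only suppressed fevers are lost.
- *That the dose 2 relative risk is materially biased.* Prophylaxis of 20% vs 5% with half of fevers suppressed would multiply it by 0.90/0.975 = 0.92. If dose 1 fever drives that gap, dose 1 fever rates must differ by at least 15 points, which the planned dose 1 relative risk would already show.
- *That a named drug is left out of the table.* SAP 4.7.5 says "Antipyretics are among medications coded under the WHO Drug dictionary ATC code N02B" and then names ibuprofen and acetaminophen. The documents do not show that either is coded elsewhere.

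**Conclusion.** The point holds as a gap in the safety and exploratory analyses. Suppressed fevers are missed, no planned fever analysis allows for them, and the antipyretic table can neither separate banned from permitted use nor be read against the fever tables' denominator. Whether the Per-Protocol set actually loses banned users depends on the medical review, so that is a possibility only.

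The size is unknown, because the documents give neither the frequency of breaches nor their effect on fever, and it is likely to be small. Under the assumed ranges, absolute fever rates are understated by 1% to 20% in relative terms. The relative risk moves only if use differs between arms, and by about 1% in the dose 1-driven illustration. The primary noninferiority conclusion is unaffected.

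**What to change.** **SAP 4.7.5 and 3.5.4.** Use the recorded reason, classified before unblinding, to split Day 1 to Day 7 antipyretic use into prophylactic, treatment and unclear, by arm, age stratum and dose. Present it on the Solicited Safety Population after the first and after the second vaccination, and change SAP 3.5.4 to match. Stating that antipyretics are selected by the named ingredients would be an optional clarification.

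**SAP 4.7.4.2.** Add one supportive fever table, any and grade 3, with relative risk. It keeps all dose periods and counts afebrile periods with prophylactic use as febrile. For the grade 3 row to be an upper bound, periods with prophylactic use that fall short of grade 3 must count there. The planned Solicited Safety Population analysis stays the main one. Dropping premedicated periods would be a poor substitute: if dose 1 fever prompts prophylaxis, it removes the more fever-prone children and can lower the rate in the same direction as the masking.

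**Cost.** A blinded review of recorded reasons, since no structured field for prophylaxis versus treatment is described, and one extra table. Parents may under-report banned use, so the bound covers recorded use only. No clinical rule changes.
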